The Effect of Early Saline Lavage on Synovial Fluid Composition Following Human
Intra-Articular Ankle Fracture

Document Date: 12/12/2024

NCT05465382

Purpose of the Study

The purpose of this study is to examine the effect of early, percutaneous, intra-articular saline lavage on the undiluted synovial fluid microenvironment during the acute phase following intra-articular fracture of the human ankle. We hypothesize that early intervention with percutaneous joint lavage in the first 0-48 hours after injury will attenuate the production of pro-inflammatory cytokines, MMP's and cartilage breakdown products compared to non-lavaged control subjects at the time of surgical fixation.

Background & Significance

Post traumatic osteoarthritis (PTOA) is a frequent cause of disability in orthopaedic trauma patients. Post-traumatic etiologies represent a disproportionately high percentage of clinically significant osteoarthritis of the ankle (65-80%) as compared to the knee and hip (2-10%). Compared to other forms of arthritis, PTOA is unique in that the timing of onset is known. As a result, there is an opportunity for studying the underlying pathogenesis at the time of injury and targeting interventions aimed at treating early disease and preventing disease progression.

Traditionally, the intraoperative restoration of anatomic joint congruity and balanced articular loading were thought to be the main factors involved in preventing the development of PTOA. However, even after anatomic reduction, intra-articular fractures of the lower extremity are still susceptible to the development of PTOA. Furthermore, the relationship between residual articular surface displacement and the development of PTOA is inconsistent in the literature. While the mechanical components of intra-articular fracture treatment have been well studied, more recent work has focused on better understanding the biological response within the joint that likely contributes to cartilage damage and the progression of PTOA.

At the time of intra-articular ankle fracture, chondrocyte death and apoptosis occur locally along the fracture edges. However, immediately thereafter, the entire joint is exposed to the inflammatory environment created by injury to the periarticular soft tissues and fractured bone edges. This gives rise to the so-called "innocent bystander" phenomenon, whereby uninjured cartilage throughout the joint is subjected to the deleterious effects of the inflammatory burden created by the healing fracture site. In 2015, Adams et al. sought to better define this inflammatory environment, and demonstrated the presence of significantly elevated levels of pro-inflammatory cytokines and extracellular matrix-degrading mediators present in the synovial fluid after intra-articular ankle fracture, which could play a role in the development of PTOA. Followup study here at Duke has demonstrated that the intra-articular composition of these inflammatory cytokines and matrix metalloproteinases (MMP's) changes over time, with evidence of in-vivo cartilage degeneration present by 10 days post-injury. Furthermore, in-vitro study has demonstrated the clear deleterious effect of synovial fluid fracture hematoma (SFFH) on chondrocyte viability on a time-based scale, with SFFH collected from 0-2 days post-injury demonstrating the greatest potential for cartilage damage.

These studies suggest that early intervention to alter the composition of the intra-articular environment may attenuate the inflammatory response, diminishing the potential for "innocent bystander" cartilage

damage and the subsequent development of PTOA. Currently, there are no therapeutics approved for the treatment of PTOA. Commercially available anti-inflammatory cytokine agents and metalloproteinase inhibitors have been shown to increase chondrocyte viability in animal and in-vitro models, however, their use is not yet approved for the treatment of PTOA in human subjects.

Saline joint lavage represents a potentially simple, low-risk and minimal-cost intervention which has not been previously studied for this purpose in human subjects. Open joint lavage at the time of definitive surgical fixation is within the standard of care, but typically occurs greater than 10 days after injury by which time cartilage degradation has already begun. Early, saline lavage during initial presentation to the clinic or emergency department may theoretically alter the progression of the intra-articular inflammatory response by evacuating the bulk of the developing synovial-fluid fracture hematoma.

The vast majority of ankle fractures present to the ER or urgent care within a day of fracture. Moreover, a large subset of these fractures require reduction (fracture setting) that is painful. It is our standard of care to perform an intra-articular lidocaine injection before reduction. We will take advantage of this standard of care needle insertion to the fractured ankle to perform saline joint lavage to diminish this early inflammatory burden.

Design & Procedures

This is a prospective randomized control trial which will be performed exclusively at Duke University Hospital (DUH). We plan to enroll 60 patients with the hopes to have 40 evaluable subjects.

After informed consent is obtained, subjects will be randomized into one of two groups as listed below.

Group 1: intra-articular saline lavage (n=30)

Group 2: no intra-articular saline lavage (n=30)

Randomization will occur by the opening of pre-prepared envelopes which will be stored in the orthopaedic resident office (HAFS Building, Room 1661). Envelopes will be labeled #1-#60. Thirty envelopes will contain a note card labeled "Group 1" and Thirty envelopes will contain a note card labeled "Group 2". Envelopes will be pre-prepared by key study personnel not involved in the consent or randomization process.

Upon informed consent, subjects will undergo physical examination, medical history assessment, vital sign measurements, and x-rays of the injured and/or contralateral ankle as part of their standard clinical care. After initial evaluation, subjects will undergo aspiration of the injured ankle joint via the standard anteromedial arthroscopy portal approach. This will be performed with sterile technique using a 16-gauge needle attached to a 10cc syringe. As previously mentioned, this standard of care needle insertion is used independent of the current study for the administration of intra-articular lidocaine for patient pain relief. The aspirate will be immediately transported to [name] lab (LSRC Building, Room B331) aliquoted and stored at -80 degrees Celsius for batch analysis.

Subjects in Group 1 will then undergo saline joint lavage as follows:

Three 10cc syringes will be filled with 10cc of sterile 0.9% normal saline.

One 10cc normal saline syringe will be injected into the ankle joint through the previously placed anteromedial 16-gauge needle.

Saline will be withdrawn from the joint into the attached 10cc syringe.

The needle will be left in place, the syringe detached, and the lavage repeated with the remaining two 10cc normal saline syringes.

After three rounds of lavage, 10cc of 1% lidocaine without epinephrine will be injected into the joint via the existing anteromedial 16-gauge needle. This will serve as an intra-articular hematoma block for patient comfort during fracture reduction and splinting.

This intra-articular lidocaine block is routinely performed as standard of care for ankle fractures presenting to the emergency department. As described, only one needle stick will be performed which will facilitate sample aspiration, lavage and lidocaine block, thus causing minimal to no additional discomfort to the patient.

Subjects in group 2 will not undergo normal saline lavage. After synovial fluid aspiration as described above, they will undergo intra-articular injection of 10cc of 1% lidocaine without epinephrine via the existing anteromedial 16-gauge needle. This will serve as an intra-articular hematoma block for patient comfort during fracture reduction and splinting.

The aspiration and lavage protocol as described above will take place in the DUH ED and be performed only by approved key study personnel.

After the initial aspiration +/- lavage and stabilization of the ankle joint, subjects will undergo a period of soft tissue rest to allow for the resolution of soft tissue swelling. This is standard of care in the treatment of periarticular lower extremity fractures. Subjects will then undergo surgical fixation when it is deemed appropriate by the Orthopaedic Trauma team, independent of this study. At the time of surgery, after tourniquet inflation, all subjects will again undergo intra-articular aspiration of the injured ankle joint. This will be performed using a 16-gauge needle attached to a 10cc syringe via a standard anteromedial arthroscopy portal approach. The aspirate will be immediately aliquoted, transported to [name] lab (LSRC building B331) and stored at -80 degrees Celsius for batch analysis.

Selection of Subjects

Adult subjects (over 18 years of age) presenting to the DUH Emergency Department with an intra-articular fracture of the ankle joint between 0-48 hours from the time of injury will be eligible for inclusion. Intra articular fracture (IAF) is defined as any fracture of the fibula or tibia in which the fracture line(s) exit into the cartilage surface of the ankle joint. Exclusion criteria include: 1) age <18yo, 2) open fracture, 3) subjects presenting >48 hours from the time of injury, 4) nonoperatively treated fractures.

Subject Recruitment and Compensation

Upon evaluation by the orthopaedic surgery team in the Duke University Hospital Emergency Department, subject eligibility will be confirmed and the study will be introduced to the subject by their treating physician. Key personnel with role of "Collaborator" will review the study in detail with the subject. Paper consent forms will be signed and stored in a key-locked file cabinet within the study coordinators office (Duke Orthopaedics Arrington, 3rd Floor, Room 3262).

We plan to enroll 60 subjects to capture 40 participants as determined by our power analysis which is detailed below. All patients who meet the above inclusion criteria will be eligible for the study. In this way, enrollment will be equitable across all demographic groups.

Risk/Benefit Assessment

As described above, this study represents minimal risk and discomfort to subjects. It is standard of care to administer an intra-articular lidocaine injection during the emergency department management of ankle fractures. We will utilize this standard of care needle insertion to the fractured ankle to perform our study related aspiration and saline lavage. In this way, no additional risk or discomfort will be incurred by the subject as a result of participation. Patients choosing not to participate will receive the normal standard of care for treatment of their injury independent of this study. Furthermore, consenting to participate in this study in no way obligates subjects to undergo surgical fixation of their ankle fracture. This decision will be made in consultation with their treating surgeon.

Risk is involved to the extent that privacy and confidentiality may be compromised. However, every reasonable effort will be made to limit breaches of privacy and confidentiality.

Subjects will not benefit directly from this study. However, data and conclusions derived from this study may improve the current understanding of post traumatic arthritis and possibly influence future patient care or study designs.

Data Analysis & Statistical Considerations

Sample Size Estimate

The study was powered (a-priori) for randomized between group differences in the primary outcome measures of Cytokines and Matrix Metalloproteinase levels collected during standardized aspirations. The study will involve two independent groups: 1) individuals with intra-articular fractures of the ankle who receive saline lavage (experimental) and 2) individuals with intra-articular fractures of the ankle who do not receive lavage (control). Differences between groups will be evaluated with a fixed effects repeated measures, analysis of covariance (RM-ANCOVA) with three dedicated time points ([1.] baseline, [2.] in the OR after anesthesia is induced (generally within 24 hours of lavage), and [3] 1 to 2 weeks post-injury). Baseline cytokines and Matrix Metalloproteinase levels will be used as a covariate control. Assuming a normal distribution for the cytokines and Matrix Metalloproteinase levels and assuming a partial theta squared effect size of 0.40 (large effect*, primarily occurring at the second time

point), we constructed a sample size estimation estimating for between groups' comparisons. With an expected 80% power, 2 time intervals*, 1 control interval, two independent groups, and a standard error of probability of 0.05, we estimated the need for a minimum sample size of 40 for statistical significance (~20 per group). We will employ intention to treat and chains equation imputation and will not oversample each group for drop outs.

Statistical Analyses

The primary outcome measure will be cytokines and Matrix Metalloproteinase levels measured at two distinct time points after injury. We will use a between groups, repeated measures Analysis of Covariance (RM-ANCOVA) to measure differences between the two designated groups. A RM-ANCOVA is used in examining the differences in the mean values of the dependent variables that are related to the effect of the controlled independent variables while taking into account the influence of the uncontrolled independent variables (baseline) over more than one time point. A p value of 0.05 will be used to measure statistical significance.

*Medium effect size required a sample size of 98

+Three time intervals would only require a sample size of 36.

Data & Safety Monitoring

The only major risk involved is the loss of confidentiality and every effort will be made to ensure this does not happen by the research staff. No followup contact with subjects will be necessary after their ankle aspirations. The results of this research will not be placed in their medical record. No PHI will leave Duke. It will not be necessary to specifically provide the subjects with any additional information, as their involvement ends with their ankle joint aspiration at the time of surgery and does not influence their longitudinal care. Furthermore, any research findings will be made available through publication. Research records containing MRN will be kept in an electronic spreadsheet on the Duke server of which access is limited to the PI and his research staff. Any electronic information will be stored on a computer that is password protected. After data collection and prior to statistical analysis, a case number will be assigned to the data and the medical record number (the only identifying data collected) will be stripped from the database. After the review is complete, publication has been accepted and all revisions have been made to the manuscript, then the study will be closed in the eIRB.

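### Randomisation is tied to consent, and nothing requires the baseline emergency department aspirate to be drawn before the arm is known; the envelopes sit in the resident office with no sealing, opacity or opening log described

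*Combined protocol and SAP*

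**What the plan says.** Allocation is described in Design & Procedures. "After informed consent is obtained, subjects will be randomized into one of two groups as listed below". The mechanism follows: "Randomization will occur by the opening of pre-prepared envelopes which will be stored in the orthopaedic resident office". There are 60 numbered envelopes, half for each group. One safeguard is stated: "Envelopes will be pre-prepared by key study personnel not involved in the consent or randomization process".

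The same section later gives the ED procedure, starting again from consent. "After initial evaluation, subjects will undergo aspiration of the injured ankle joint via the standard anteromedial arthroscopy portal approach". This applies to both groups. The next step is specific to one arm: "Subjects in Group 1 will then undergo saline joint lavage as follows". Lavage and the lidocaine block use the needle already placed for the aspiration. The operator is described only as approved key study personnel.

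Subject Recruitment and Compensation says that the orthopaedic team evaluates patients in the ED and that "the study will be introduced to the subject by their treating physician"; a collaborator then goes through it in detail. Signed consent forms go into a locked cabinet in the coordinator's office.

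Sample Size Estimate makes the baseline levels the covariate in the repeated-measures ANCOVA and plans intention to treat with chained-equation imputation.

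**The concern.** The ED aspirate does two jobs. It supplies the baseline covariate. It also removes fluid from the joint, and the plan's reason for lavage is that clearing the early haematoma may change the later inflammatory course. For control subjects this aspiration is the only evacuation before surgery. The procedure fixes the portal, needle and syringe, but sets no target volume or stopping point for the draw.

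An operator who knows the arm could draw more fully when no lavage will follow, or less fully when it will. Either would affect both the covariate and the control condition. Adjusting for a baseline value that knowledge of the allocation has influenced does not remove that influence.

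Concealment is a second exposure. Independent preparation of the envelopes does not secure their storage or opening, and the resident office may be within reach of the orthopaedic team that recruits. Third, if the envelope is opened first, a failed tap produces a randomised subject with no measured baseline.

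**Working it through.** **Order of events.** The documents give two sequences, both starting at consent:

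- Allocation: consent, then randomisation by envelope.
- Procedure: consent, evaluation, aspiration in both arms, then lavage in Group 1.

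Neither is placed against the other. Three features favour opening the envelope before the tap: randomisation is presented first and triggered by consent; group membership is treated as known once the aspirate is drawn, with no envelope step in between; and the envelopes are in a named office while the procedure runs in the ED through a needle left in place. None of these is a statement of the order.

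**What is not described.** The documents do not say who opens the envelope, whether envelopes are sealed and opaque or used in numerical order, whether openings are logged, whether the operator is masked, or what happens after a failed tap.

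**The plan's own sample size.** From Sample Size Estimate: effect size 0.40, two measurements (m = 2), two groups, alpha 0.05, power 80%. The correlation between measurements is not given; I assume rho = 0.5. For the between-groups F test with 1 and N - 2 degrees of freedom, the noncentrality is f² × N × m / (1 + (m - 1) × rho). With f = 0.40 and N = 40 this is 0.16 × 40 × 2 / 1.5 = 8.53, and power is 0.812. The stated 40 is reproduced. The same model gives 98 for f = 0.25 and 36 for m = 3, matching both footnotes. The 0.40 must have been used as Cohen's f; read literally as a partial eta squared it gives only 12. Other assumed correlations give 28 (rho 0), 34 (0.3), 44 (0.7) and 50 (0.9).

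**Failed taps.** The failure rate q is not in the documents; I show a range. Enrolling 60 for 40 evaluable implies a loss of 1 - 40/60 = 33.3%. If failed taps come on top of that loss, complete cases are 60 × (1 - q) × 2/3. If instead only patients with a collected aspirate are randomised, the consents needed are 60/(1 - q), rounded up.

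| Assumed q | Failed of 60 | Complete cases, tap after randomisation | Power | Consents to randomise 60 after the tap |
|---|---|---|---|---|
| 0% | 0 | 40 | 0.81 | 60 |
| 5% | 3 | 38 | 0.79 | 64 |
| 10% | 6 | 36 | 0.77 | 67 |
| 20% | 12 | 32 | 0.72 | 75 |
| 25% | 15 | 30 | 0.69 | 80 |

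If failed taps are already inside the one-third allowance, 40 remain and power stays at 0.81. The power column counts complete cases only. Under the planned imputation a failed-tap subject stays in the analysis, and a failed ED tap does not prevent the aspirate at surgery, so the column is pessimistic.

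**The case against.** The strongest reply is that the order is not written down. Aspiration is the same in both arms and the first arm-specific step comes after it, so the text also permits opening the envelope between aspirate and lavage. That stands. A reader might infer that the protocol has the operator take the baseline sample knowing the arm. The documents do not say so: the operator is not said to be a resident, nor the person who opens the envelope.

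A reader might also infer that recruiters can see the allocations. Neither the treating physician nor the collaborator is said to have access to the resident office, and the envelopes are prepared by independent personnel. Sealing and custody are undescribed, which does not show that they are absent.

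A third tempting reading is that failed taps become losses from the analysis. Intention to treat with imputation keeps those subjects in. What remains is that their baseline is imputed, not measured.

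Finally, the outcomes are laboratory levels from batch analysis, which leave less room for assessor judgement, and the documents do not show that the amount of fluid drawn changes measured levels. The bias is therefore a plausible mechanism whose size and direction are unknown.

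These points limit the claim to what the plan permits. They do not answer why an avoidable exposure is left open when a short procedural statement would close it.

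**Conclusion.** The concern holds as a gap in the stated procedure that should be closed. Followed as written, the plan allows the arm to be known before the covariate sample is drawn, and that sample is also the control arm's only evacuation before surgery. It also keeps allocations where the recruiting team may be able to reach them. That the envelope is opened first is the likeliest reading, but an inference.

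The case rests on bias and concealment, which the documents do not allow me to size. The effect on power is secondary: none if failed taps are inside the 60-to-40 allowance, and at most a fall from 0.81 to 0.79-0.77 if 5-10% of taps fail on top of it. Those figures assume the failure rate, a correlation of 0.5 and a complete-case count. The required sample size of 40 is not affected.

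**What to change.** State in Design & Procedures that:

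- the next sequentially numbered, sealed, opaque envelope, or a web allocation, is opened only after consent, confirmed eligibility and collection of the ED aspirate, by a team member already present;
- allocations are held outside the resident office, for example by the study coordinator, with a log of each opening;
- a patient whose ED tap fails is not randomised, and such patients are counted and reported.

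If envelopes are already opened after the aspirate, one sentence saying so settles the order. If there is a reason to open them earlier, the plan should give it, and say how the draw is kept the same in both arms and how a failed tap is handled.

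The cost is mostly wording and bedside logistics. Saline must be ready for every subject, the allocation must be available at the ED bedside, and a second person opens it during a short pause with the needle in place. Failed-tap patients leave the randomised population, which narrows it to patients with a collectable aspirate but does so before allocation. Slightly more consents are needed: about 64-67 to randomise 60 if 5-10% of taps fail, an assumed rate.

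### The claim of no added risk does not follow from the shared needle, and the visible plan describes no recording of physical harms by arm

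*Combined protocol and SAP*

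**What the plan says.** The Risk/Benefit Assessment opens with the statement that "this study represents minimal risk and discomfort to subjects". It explains that the needle placed for the routine lidocaine block will also serve the study aspiration and lavage, and concludes that "no additional risk or discomfort will be incurred by the subject as a result of participation". The one risk it then names is informational: "Risk is involved to the extent that privacy and confidentiality may be compromised".

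Design & Procedures sets out the steps. In the emergency department (ED), both groups are aspirated before the block. Group 1 then has three cycles of 10cc saline injected and withdrawn: "The needle will be left in place, the syringe detached, and the lavage repeated with the remaining two 10cc normal saline syringes". Lidocaine follows the third cycle. At surgery, "all subjects will again undergo intra-articular aspiration of the injured ankle joint". The same section puts the extra discomfort of the single needle stick at little or none.

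Data & Safety Monitoring begins "The only major risk involved is the loss of confidentiality". It adds "No followup contact with subjects will be necessary after their ankle aspirations" and says of subjects that "their involvement ends with their ankle joint aspiration at the time of surgery". The rest of the section deals with data storage, de-identification and study closure.

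**The concern.** The statement of no added risk depends on one needle doing two jobs. Sharing the needle removes an extra stick in the ED. It does not remove what is done through the needle, and it cannot apply to an aspiration performed later at surgery. The statement also disagrees with the two milder descriptions elsewhere in the same document.

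This matters because the monitoring section appears to rest on the same premise. If the only risk is to confidentiality, there is nothing physical to record. Background & Significance describes lavage as potentially low-risk and as not previously studied for this purpose in humans, and subjects are told to expect no direct benefit. Run as written, the trial could report a biomarker result with no harm count in either arm, and a joint infection after lavage would prompt no step described in this plan.

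**Working it through.** **Study steps against the stated reason** (Design & Procedures; Risk/Benefit Assessment)

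| Step | Group 1 | Group 2 | Covered by the shared-needle argument? |
|---|---|---|---|
| Needle insertion in the ED | yes | yes | Yes, it is routine care |
| Aspiration before the block | yes | yes | The stick is, the aspiration is not |
| Saline in and out, 3 × 10cc = 30cc, before lidocaine | yes | no | The stick is, the lavage is not |
| Aspiration at surgery | yes | yes | No, it is a separate needle placement |

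Only the first row is fully covered. The lavage cycles also come before the joint anaesthetic, so the block cannot be what keeps them comfortable.

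**Exposure in the ED, counted as syringes**

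- Group 1: 1 aspiration + 3 saline + 1 lidocaine = 5 syringes, so 4 changes.
- Group 2: 1 aspiration + 1 lidocaine = 2 syringes, so 1 change.
- Block outside the study: 1 syringe and 0 changes. This is an assumption, since the documents do not describe how the routine block is given.

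The needle stays in place, so this is one entry into the joint with several connections. The counts show added handling and are not a harm rate.

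**Search for a harm-recording step.** The Sample Size Estimate and Statistical Analyses name cytokine and matrix metalloproteinase levels as the outcomes. The Risk/Benefit Assessment names privacy. Data & Safety Monitoring names confidentiality. No visible section defines an adverse event or complication, or gives a collection window, a by-arm count or a reporting route.

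**What a by-arm count could show.** The plan states no harm rate, so there is no figure to reproduce. The denominators are its own: 30 per group enrolled, and about 20 per group if 40 are evaluable.

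Chance of at least one event among 30 lavaged subjects = 1 − (1 − p)^30, with p assumed:

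- p = 1%: 1 − 0.99^30 = 0.260
- p = 2%: 1 − 0.98^30 = 0.455
- p = 5%: 1 − 0.95^30 = 0.785

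Upper 95% limit with zero events:

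- One-sided, n = 30: 1 − 0.05^(1/30) = 0.095
- One-sided, n = 20: 1 − 0.05^(1/20) = 0.139
- Two-sided exact, n = 30: 1 − 0.025^(1/30) = 0.116

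**Who would be missed.** Sixty are enrolled to obtain 40 evaluable. The Risk/Benefit Assessment says that consent does not oblige a subject to have surgery. A lavaged subject who is not operated on has no planned study contact after the ED, so a harm count tied only to surgery would leave that subject out.

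**The case against.** The strongest reply is that the hazard is low and the subjects are not unobserved. The plan specifies sterile technique, sterile saline and approved personnel. Subjects remain under orthopaedic care, and the joint is entered again at surgery. That aspiration follows tourniquet inflation, is the same in both arms, and comes at an operation where open joint lavage is already standard, so it cannot by itself create a difference between arms. Naming confidentiality as the only major risk leaves room for minor ones. The study is under institutional review, whose reporting rules are not in these documents, and the consent pages were removed.

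Much of this stands. It limits the point to what the visible plan describes, and it rules out three stronger readings that a reader might infer:

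- *That the lavage is harmful.* The documents contain no evidence of harm, only of added exposure.
- *That harms could not be detected or matched to arm.* Research records carry the medical record number until data collection is finished, so linkage is available throughout enrolment. What is missing is a written recording step.
- *That the syringe changes amount to repeated joint entries.* The needle is left in place.

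The reply does not rescue the statement of no added risk. Sterile technique lowers risk but does not bring it to zero, and routine care does not produce a count by randomized group.

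**Conclusion.** The point holds, as a cheap improvement. The no-added-risk statement is not supported by the reason given and conflicts with the document's own milder wording. The monitoring section covers confidentiality and data handling, and no visible section describes recording or reporting physical harms by arm.

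The primary biomarker comparison is unaffected; a reader who infers otherwise would find nothing in the documents to support it. The gap concerns subject protection and what may be said about risk afterwards. Its size is limited by the trial's size: at assumed true rates of 1% to 5%, a log would have a 26% to 79% chance of capturing at least one event in the lavage arm, and zero events would leave rates up to about 9.5% (30 subjects) or 13.9% (20 subjects) open. The event rates are assumptions. The conclusion also assumes that institutional rules and consent pages outside these documents do not already provide a by-arm harm record.

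**What to change.** In the Risk/Benefit Assessment, replace the claim of no additional risk with one of minimal additional risk or discomfort. Name the aspiration before the block, Group 1's three saline cycles before lidocaine, and the aspiration at surgery. Bring the discomfort wording in Design & Procedures into line.

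In Data & Safety Monitoring, add a paragraph such as:

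*For both groups, study staff will record procedure-related events in the ED, including any lavage stopped early and the reason. At the surgical aspiration, or by chart review at a fixed time after the ED procedure for subjects who do not have surgery, they will record suspected or confirmed infection in that ankle joint, and unplanned visits or antibiotics for that ankle. Recording will be complete before the medical record number is removed. Counts will be reported by randomized group with exact confidence intervals and no hypothesis test. Confirmed joint infections will be reported to the IRB under its rules.*

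The investigator should set the fixed time. Chart review to 30 days after surgery can be optional, because infections after the operation may be due to the operation in either arm. An automatic enrolment pause after a single event is not needed; that decision can rest with the IRB.

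The cost is at most 60 chart checks. At an assumed 10 to 15 minutes each, that is 60 × 10 = 600 to 60 × 15 = 900 minutes, or 10 to 15 hours, and less if review is confined to subjects without surgery. A consent line permitting chart review may be needed. There are no extra visits, procedures or subjects, and the primary analysis does not change.
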